5.6.4.6 Growth and Development

IGF-1 levels will be analyzed as part of the clinical laboratory testing. IGF-1 levels will be summarized on a continuous scale, including change from baseline, by treatment arm.

For the blinded phase only, change from baseline to the end of treatment visit for IGF-1 levels will also be plotted against the Tanner Stages, weight, and height recorded at baseline.

The pubic hair growth (both sexes), genital (males only) and breast (females only) development of all adolescent patients (i.e., 10 to less than 18 years of age at the time of signing the informed consent form, or earlier if clinically indicated by onset of menarche or other signs of precocious puberty) will be assessed using Tanner Staging. The patients will undergo a discreet physical examination and be assigned a value under each category of Pubic Hair Growth (both sexes), Genitals (male patients only), and Breasts (female patients only).

Tanner Stages will be summarized on a categorical scale, by treatment arm.

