	additional Supplemental Adverse Event Form and Site Classification Form (investigator only) following further discussion of the event(s) with the patient/caregiver. The second trigger that will require the investigator or study coordinator to discuss abuse potential signals with the patient/caregiver is drug accountability issues regarding overuse of the IMP or missing bottles. Irrespective of the above, all patients/caregivers will be interviewed at their final dosing visit of the blinded phase (Visit 10 or 11) and again at their final dosing visit of the OLE (Visit B10 or B11). A Study Medication Use and Behavior Survey will be completed by the investigator or study coordinator. A formal Adjudication Committee will be appointed and assigned to this initiative to classify triggered cases. The Adjudication Committee will meet on a periodic basis to review and assess all of the information collected on triggered cases.
Statistical	Blinded Phase:
Considerations	Each of the primary and secondary endpoints will be described and compared between treatment groups, using appropriate statistical methods, over the 16-week, double-blind maintenance and titration period.
	Statistical hypothesis testing will be performed on the primary endpoint and other endpoints as appropriate. Each endpoint, including the primary will have 2 comparisons against placebo (25 mg/kg/day GWP42003-P and 50 mg/kg/day GWP42003-P vs. placebo). Also, 3 key secondary endpoints have been defined. The primary and key secondary endpoints will be tested with their Type I error controlled by use of a hierarchical gate-keeping procedure. One must reject the null hypothesis of an endpoint at the level of 0.05 (2-sided) to test the hypothesis of the subsequent endpoint in the sequence at the level of 0.05 (2-sided). If a null hypothesis is not rejected then testing will stop and all subsequent analyses will be declared not statistically significant. The secondary endpoints will be tested hierarchically, starting with the key secondary endpoints. No multiplicity adjustments will be made for all other secondary endpoints. All other statistical tests will be two-tailed and carried out at the 5% level of significance. All safety data will be summarized using appropriate statistical methods. Open-label Extension: All data collected during this study will be summarized across

[figure not shown]

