# 13.6.3 Secondary Endpoint(s)

The following endpoints will be compared between treatment groups over the treatment period, for the blinded phase, and during the open-label extension phase relative to the pre-randomization baseline of the blinded phase:

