#### **Blinded Phase:**

The number of patient responders (including the key secondary endpoint) and the number of patients seizure-free will be summarized and analyzed using a Cochran–Mantel–Haenszel test stratified by age group. In addition, the difference in proportions and the odds ratio, together with 95% CIs, comparing the treatment groups will be presented.

For number of seizure-free days, use of rescue medication, number of episodes of *status epilepticus* (only if there is a sufficient number of patients with data), Vineland-II, Wechsler scales, CBCL, ABCL, SCQ, QOLCE and QOLIE-31-P scores, the data will be summarized at baseline and over the treatment period, and at each time-point (or 28-day period, as appropriate) during the maintenance period. Changes from baseline to the average over the treatment period (or at end of study) will be analyzed using ANCOVA (or appropriate non-parametric methods if data are found to be not normally distributed). The models will include baseline and age group as covariates and treatment group as fixed factor. The treatment difference, together with the 95% CIs will be presented.

The changes in composite focal seizure score, change in total seizures, the number of seizures by subtype and the number of 'other' seizures will be analyzed using the same analysis as the primary endpoint.

SGIC-SD/CGIC-SD, SGIC/CGIC and PGIC assessments recorded at the end of treatment will be analyzed with ordinal logistic regression using the proportional odds model.

Changes from baseline for IGF-1 levels will be summarized by treatment group and plotted against the Tanner Stages, weight, and height.

Tanner Stages will be evaluated and summarized descriptively at each time-point in terms of frequency and proportions. Number (%) of patients with changes in Tanner Stages will be summarized by treatment group.

In order to explore the robustness of the primary analysis, further sensitivity analysis (in addition to that already detailed in Section 13.6.2.1) may be specified in the SAP.

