2.2 Secondary Objectives

Blinded Phase:

- To evaluate the effect of GWP42003-P compared with placebo on antiepileptic measures.
- To evaluate the effect of GWP42003-P on growth and development (in patients less than 18 years old) compared with placebo.
- To evaluate the effects of GWP42003-P on quality of life compared with placebo.
- To evaluate the safety and tolerability of GWP42003-P compared with placebo.

Open-label Extension:

- To evaluate the long term effects of GWP42003-P, as add-on therapy, on antiepileptic measures.
- To evaluate the long term effect of GWP42003-P on growth and development (in patients less than 18 years old).
- To evaluate the long term effects of GWP42003-P on quality of life.
- To evaluate the long term safety and tolerability of GWP42003-P.

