3.3.2 Secondary Efficacy Endpoints

Blinded Phase:

The following endpoints will be compared between treatment arms over the 16-week, double-blind treatment period (all changes relative to baseline):

Key:

1. Number of patients considered treatment responders defined as those with a $\geq 50\%$ reduction in TSC-associated seizure frequency (see Section 5.1.3.7).
2. Change in Caregiver Global Impression of Change (CGIC) or Subject Global Impression of Change (SGIC) score.
3. Change in total seizures.

Other:

Antiepileptic Efficacy Measures:

- Number of patients considered treatment responders defined as those with a $\geq 25\%$, $\geq 50\%$, $\geq 75\%$ or 100% reduction in TSC-associated seizure frequency.
- Number of patients experiencing a $> 25\%$ worsening, $- 25$ to $+ 25\%$ no change, 25–50% improvement, 50–75% improvement or $> 75\%$ improvement in TSC-associated seizure frequency.
- Change in number of TSC-associated seizure-free days.
- Change in number of ‘other’ seizures (absence, myoclonic, focal sensory and infantile/epileptic spasms).

Growth and Development (in patients less than 18 years old):

- Change in serum insulin-like growth factor-1 (IGF-1) levels.
- Change in Tanner Staging score (for patients aged 10–17 [inclusive]).

Quality of Life:

- Changes in the Quality of Life in Childhood Epilepsy (QOLCE; patients 2–18 years) or Quality of Life in Epilepsy (QOLIE-31-P; patients 19+ years) score.
- Change in Physician Global Impression of Change (PGIC) score.

Safety and Tolerability:

- AEs.
- Clinical laboratory parameters.
- 12-lead electrocardiogram (ECG).
- Physical examination parameters.
- Vital signs.
- Columbia-Suicide Severity Rating Scale (C-SSRS: 19+ years) or C-SSRS Children’s (6–18 years) score, where applicable.
- Number of inpatient hospitalizations due to epilepsy.
- Abuse liability.
- Effects on menstruation cycles (in females).

Open Label Extension:

The following endpoints will be assessed relative to the pre-randomization baseline of the blinded phase:

Key:

- Percentage change in number of TSC-associated seizures (average per 28 days).
- Number of patients considered treatment responders defined as those with a $\geq 50\%$ reduction in TSC-associated seizure frequency.
- Change in CGIC or SGIC score.
- Change in total seizures.

Other:

Antiepileptic Efficacy Measures:

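### Change in IGF-1 is listed as an endpoint to be compared with placebo, but neither document plans a between-arm estimate or interval for it

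*SAP*

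**What the plan says.** **Objective.** Protocol 2.2 and SAP 2.2 set as a secondary objective: "To evaluate the effect of GWP42003-P on growth and development (in patients less than 18 years old) compared with placebo".

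**Endpoint.** SAP 3.3.2 lists "Change in serum insulin-like growth factor-1 (IGF-1) levels" under growth and development, and its lead-in reads "The following endpoints will be compared between treatment arms over the 16-week, double-blind treatment period". Protocol 4.1.2 has the same structure. In the protocol's statistics chapter, section 13.6.3 opens with "The following endpoints will be compared between treatment groups over the treatment period, for the blinded phase", and IGF-1 is in the list that follows. The synopsis says "Each of the primary and secondary endpoints will be described and compared between treatment groups, using appropriate statistical methods". Protocol 13.6 and SAP 5.5.1 add that every endpoint has two comparisons against placebo, one per dose.

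**Method.** Protocol 13.6.3 says "Changes from baseline for IGF-1 levels will be summarized by treatment group and plotted against the Tanner Stages, weight, and height". SAP 5.6.4.6 says "IGF-1 levels will be summarized on a continuous scale, including change from baseline, by treatment arm", with plots of the change to the end of treatment visit against baseline Tanner stage, weight and height. Neither the text nor the titles of Figures 14.1.1 to 14.1.3 in SAP Appendix 6 say that the plots are split by arm. Appendix 6 names no IGF-1 analysis table.

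**The concern.** The objective is comparative, and the endpoint lists say a comparison will be made, but the methods stop at description by arm. The other growth measures do not fill the gap. Tanner stage is tabulated by category (Protocol 13.6.3, SAP 5.6.4.6), and height and weight are summarized with the vital signs (SAP 5.6.4.3).

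The patients concerned are growing, and some are going through puberty, so IGF-1 may change over 16 weeks without any drug effect. The randomized contrast with placebo separates the two. If no contrast is prespecified, the study report need not contain one. Anyone who wants it must build it afterwards, with free choice of adjustment and timepoint. Blood is drawn for IGF-1 at Visits 3 and 10 in every patient under 18, so the data for a planned estimate will exist.

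**Working it through.** **1. Stated intention against specified method (blinded phase)**

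| Endpoint | Status | Planned analysis against placebo |
|---|---|---|
| Seizure-free days (SAP 5.5.3.2.2) | secondary | ANCOVA, difference, 95% CI |
| QOLCE, QOLIE-31-P (SAP 5.5.3.2.4, 5.5.3.2.5) | secondary | ANCOVA, difference, 95% CI |
| Rescue medication, Wechsler, SCQ (SAP 5.5.4.3, 5.5.4.7, 5.5.4.9) | exploratory | ANCOVA, difference, 95% CI |
| IGF-1 (SAP 5.6.4.6) | secondary | none; summary by arm and plots |
| Tanner stage (SAP 5.6.4.6) | secondary | none; categories by arm |

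Some exploratory continuous endpoints thus have a planned contrast with placebo, while this secondary one does not.

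**2. The documents' own figure**

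The documents give no sample-size or precision figure for IGF-1. Their one calculation is for the primary comparison: 70 per arm, reductions of 15% and 50%, SD 60%, two-sided 5% Wilcoxon test, 90% power. It reproduces with Noether's formula:

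- P(X<Y) = Φ(35/(60√2)) = 0.660.
- Power at 140 patients = Φ(√(3 × 140) × 0.160 − 1.96) = 90.6%.

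Only the 70 per arm is carried forward. Pooling the two placebo groups of the 2:2:1:1 allocation gives three equal arms.

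**3. What a planned contrast would deliver**

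Assumptions, none of them in the documents: 60% to 80% of patients are under 18; 10% of IGF-1 pairs are missing; the correlation r between baseline and end of treatment is 0.5 to 0.8; the SD is the same at both visits.

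Pairs per arm: 70 × 0.6 × 0.9 ≈ 38; 70 × 0.7 × 0.9 ≈ 44; 70 × 0.8 × 0.9 ≈ 50.

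95% CI half-widths in SD units (normal approximation):

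- ANCOVA: 1.96 × √(2(1 − r²)/n)
- Difference of change scores: 1.96 × √(4(1 − r)/n)

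| n per arm | r | ANCOVA | Change scores |
|---|---|---|---|
| 38 | 0.5 | 1.96 × √(1.50/38) = 0.39 | 1.96 × √(2.0/38) = 0.45 |
| 44 | 0.5 | 1.96 × √(1.50/44) = 0.36 | 1.96 × √(2.0/44) = 0.42 |
| 50 | 0.8 | 1.96 × √(0.72/50) = 0.24 | 1.96 × √(0.8/50) = 0.25 |

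The variance ratio is (1 + r)/2, which is 0.75 at r = 0.5 and 0.90 at r = 0.8. For a shift of 0.5 SD (an illustration, not a documented target) at n = 44 and r = 0.5, power = Φ(0.5/SE − 1.96). This gives 77% for ANCOVA (SE 0.185) and 65% for change scores (SE 0.213).

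As a check on the range of n, a comparison that ignores baseline has half-width 1.96 × √(2/n). That is 0.33 SD if all 70 per arm are under 18 and 0.47 SD if only 35 are.

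**The case against.** The strongest reply is that the descriptive treatment of IGF-1 is itself prespecified. Protocol 13.6.3 names the endpoints that get ANCOVA, leaves IGF-1 out, and says what is done with it instead. SAP 5.6.4.6 follows. This stands: the SAP does not depart from the protocol. A reader might take the silence of SAP 5.8 as an unrecorded dropping of an analysis, but the two method texts agree and nothing was dropped. The mismatch between stated intention and method lies inside both documents.

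Second, *compared* is used loosely. The lead-in in SAP 3.3.2 also covers laboratory values, ECG and vital signs, which get no ANCOVA. The seizure-change categories are only summarized by arm too (SAP 5.5.3.2.1), and testing is promised only where appropriate (SAP 5.5.1). So IGF-1 is not the only continuous measure on the secondary list without a model, and a missing p-value is defensible. The missing difference and interval are harder to defend. Growth and development has its own comparative objective and is listed apart from safety and tolerability, and the list in Protocol 13.6.3 does not contain the safety measures.

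Third, a reader might infer that the trial could neither show nor bound an effect on IGF-1. The documents do not support that. SAP 5.1 gives n, mean and SD by arm, and adds a pooled placebo column where safety tables split placebo by volume. A crude difference and interval can therefore be derived. What is lost is a planned contrast, adjusted for baseline and for the age group used in the stratification.

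**Conclusion.** The point holds as a gap between the stated comparison and the specified method, present in both protocol and SAP. No growth measure has a planned estimate or interval against placebo, although the objective is worded as a comparison with placebo.

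The size is modest. IGF-1 is a non-key secondary endpoint outside the hierarchy, so neither the primary conclusion nor Type I error control is affected. On the assumed inputs, ANCOVA narrows the half-width by about 0.01 SD (0.25 to 0.24) at the favourable end and 0.06 SD (0.45 to 0.39) at the other. The main gain is that the contrast is fixed before unblinding and reported. The SD-unit figures depend on the assumed share of patients under 18, missing rate and correlation. The finding that no contrast is planned does not depend on them. This is a cheap improvement, not a flaw that threatens the trial.

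**What to change.** In SAP 5.6.4.6 add, for patients under 18 in the blinded phase: change in IGF-1 from baseline to the end of treatment visit will be analysed by ANCOVA with baseline IGF-1 and stratified age group as covariates and treatment arm as fixed factor. Report the least squares mean difference and 95% CI for each GWP42003-P arm against pooled placebo, and state that these comparisons are outside Type I error control. This is the model and timepoint of SAP 5.5.3.2.4, and the timepoint matches the existing IGF-1 plots. Add the table to Appendix 6 and keep the current summaries and plots.

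The cost is one paragraph and one table from an existing program, with no new data, visits or patients. The downside is one more unadjusted secondary comparison to report.

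If the team prefers description only, the lesser remedy is to say so in Protocol 13.6.3 and SAP 3.3.2, so that the endpoint lists no longer promise a comparison for growth endpoints.

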5.6.4.7 Menstruation

Menstruation details will be summarized as appropriate, including any changes in normal cycles, by treatment arm.

5.7 Other Measures

5.7.1 Concomitant Medication

Medications will be coded using the World Health Organization Drug Dictionary, Version September 2016.

A medication will be considered concomitant for each phase if it has a start date on or after the first dose of IMP for the corresponding phase or if it was started prior to the first dose of IMP and was ongoing. If a medication has a partial or missing start/stop date and it is unclear from the date whether the medication was taken after the first dose of IMP then it will be considered concomitant.

For summaries and listings of medications the following approach will be used to determine the Anatomical Therapeutic Chemical (ATC) term to be presented:

- If coded to level 4 then the level 4 coded term will be presented.
- If coding is not performed at level 4 but level 3 coding is present, then level 3 coded term will be presented.
- If coding is not performed at level 3 but level 2 coding is present, then the level 2 coded term will be presented.
- If coding is not performed at level 2 but level 1 coding is present, then the level 1 coded term will be presented.

Summaries of each of the following by ATC term and preferred term will be summarized by absolute counts (n) and percentages (%), separately for the blinded and OLE phase (unless stated otherwise):

- History of AEDs (blinded phase only);
- Concomitant AEDs;
- Concomitant rescue medications; and
- Other concomitant medications.

The ATC term, preferred term, reported generic name and reported brand name will be listed.

An additional summary table will be produced for concomitant antiepileptic therapies, displaying the number and percentage of patients with a vagus nerve stimulation device or on a ketogenic diet.

The start day and stop day will be included in the listing according to Section 5.1.2. If the date is partial and the exact day is unknown then the text 'pre' or 'post' will replace the start or stop day if it is clear from the partial date that the medication started or stopped prior to or after the first dose of IMP.

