#### 9.1.2 Open-label Extension

Patients who successfully complete the blinded phase will be invited to participate in the OLE when they reach the End of Treatment visit (Visit 10) of the blinded phase. They will be issued with the OLE patient information and informed assent or the patient/parent(s)/legal representative information and informed consent (as applicable). Following adequate time to discuss the study with the investigator, nurse, relatives or caregiver, patients/parent(s)/legal representatives who provide written informed consent/assent at Visit B1 will be enrolled into the OLE. The OLE period will last for a maximum of 1 year; however, patients in the US and Poland may have the opportunity to continue in the OLE beyond this.

On-label use of mTOR inhibitors (for the treatment of seizures or tumors) and general anesthesia are permitted in the OLE phase of the trial.

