5.4.3 Demographic Data and Baseline Characteristics

The following demographic data will be summarized by treatment arm and overall for the safety, ITT, PP and OLE safety analysis sets:

- Age (years);
- Age group (1–6 years, 7–11 years, 12–17 years and 18–65 years);
- Sex;
- Race;
- Country;
- Region (US, Rest of the World);
- Weight at baseline (kg);
- Height at baseline (cm);
- Body mass index at baseline (kg/m²).

Age will be calculated as:

$$(\text{Date of screening} - \text{date of birth}) \div 365.25.$$

The following baseline characteristics will be summarized by treatment arm and overall for the safety, ITT, PP and OLE safety analysis sets:

- Average number of TSC-associated seizures per 28 days during baseline.
- Average number of total seizures per 28 days during baseline.
- Number of patients with seizures during the baseline period, by seizure type.
- Number of AEDs a patient has used, prior to the trial and is no longer taking.

- Number of AEDs a patient is currently taking.
- Total number of prior and current AEDs.
- Number of patients taking clobazam (Yes, No, and if no, Prior).
- Number of patients taking valproic acid (Yes, No, and if no, Prior).
- Number of patients taking levetiracetam (Yes, No, and if no, Prior).
- Number of patients taking vigabatrin (Yes, No, and if no, Prior).

The number of prior AEDs no longer taking will be taken from the 'History of antiepileptic medications and therapies' CRF page. The number of AEDs a patient is currently taking is based on the 'Concomitant antiepileptic medications' CRF page. If a patient has a medication listed on both the 'History of antiepileptic medications and therapies' and 'Concomitant antiepileptic medications' CRF pages and the medication is considered concomitant (see Section 5.7.1) for the double-blind phase, then this will not be included in the number of prior AEDs no longer taking. AEDs starting after the last dose of IMP during the double-blind phase will not be counted.

Patients taking the same AED type, but where the AED were coded to different generic terms will be counted only once within the AED type. For example, valproate sodium, valproic acid, valproate semisodium and ergenyl chrono will all be counted as valproic acid and counted once under that term.

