The number of patients taking clobazam is defined as the number of patients taking clobazam at any point during baseline period or treatment period. The same definition will apply for the number of patients taking each of the other AEDs. The number of patients taking other AED types will also be presented if the overall frequency of patients taking the AED is >25%.

Previous cannabis use will be included within the baseline characteristics listing.

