5.6.2 Adverse Events

All reported AEs will be classified by system organ class (SOC), preferred term and lower level term using Version 19.1 of MedDRA.

Summaries will be presented by treatment arm as well as SOC and preferred term.

A blinded phase treatment emergent AE (TEAE) is defined as an AE with a start date on or after the first dose of IMP during the blinded phase up to and including the date of first dose of the OLE phase (OLE Day 1). An OLE phase TEAE is defined as an AE with a start date on or after the OLE Day 1. If an AE has a partial start date and it is unclear from the partial date (or the stop date) whether the AE started prior to or post first dose of IMP then the AE will be considered treatment emergent and if it is unclear which phase the event started, it will be assigned to both phases. If the start date of the AE is the same as the date of first dose of IMP from the blinded phase and the plausible relationship to IMP is marked on the CRF as "Prior to study medication" then the AE will not be considered treatment emergent.

An AE will be considered treatment-related if the plausibility relationship to trial medication is recorded on the CRF as 'yes'. If the data on plausibility relationship to trial medication is missing then the AE will be considered treatment-related.

An AE will be considered leading to permanent discontinuation of IMP if the action taken with IMP is recorded on the CRF as 'study medication stopped' or the outcome is recorded on the CRF as 'patient died'.

An AE will be considered leading to IMP dose reduction excluding permanent discontinuation if the action taken with IMP is recorded on the CRF as 'dose reduced', 'dose reduced temporarily' or 'study medication interrupted'.

An AE will be considered leading to temporary IMP dose reduction if the action taken with IMP is recorded on the CRF as 'dose reduced temporarily'.

An AE will be considered leading to permanent IMP dose reduction excluding permanent discontinuation if the action taken with IMP is recorded on the CRF as 'dose reduced'.

An AE will be considered fatal if the outcome is recorded on the CRF as 'patient died'.

The following summaries will be generated separately for the blinded and OLE phase (counts are by patient unless specified otherwise):

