Appendix 6 List of Tables, Listings and Figures

Table 17 List of Blinded Phase Tables

Table Number	Title	Analysis Set
Table 1.1.1	Summary of Patient Disposition – Number of Patients Screened and Randomized by Site	All Screened Patients
Table 1.1.2	Summary of Patient Disposition – Number of Patients Screened and Randomized by Country	All Screened Patients
Table 1.2	Summary of Patient Disposition – Reasons for Screen Failure	All Screened Patients
Table 1.3.1	Summary of Patient Disposition by Site	All Randomized Patients
Table 1.3.2	Summary of Patient Disposition by Country	All Randomized Patients
Table 1.4	Summary of Overall Patient Disposition	All Randomized Patients
Table 2.1	Summary of Important Protocol Deviations	All Randomized Patients
Table 2.2	Summary of Analysis Sets	All Randomized Patients
Table 3.1.1	Summary of Demographic Data	Safety Analysis Set
Table 3.1.2	Summary of Demographic Data	ITT Analysis Set
Table 3.1.3	Summary of Demographic Data	PP Analysis Set
Table 3.2.1	Summary of Baseline Characteristics	Safety Analysis Set
Table 3.2.2	Summary of Baseline Characteristics	ITT Analysis Set
Table 3.2.3	Summary of Baseline Characteristics	PP Analysis Set
Table 4.1.1	Summary of Seizure Types No Longer Occurring	Safety Analysis Set
Table 4.1.2	Summary of Current Seizure Types	Safety Analysis Set
Table 5.1	Summary of Previous Significant Non-Epilepsy Medical or Surgical History Now Resolved	Safety Analysis Set
Table 5.2	Summary of Significant Non-Epilepsy Medical or Surgical History – Current Conditions	Safety Analysis Set
Table 6.1	Summary of History of Antiepileptic Drugs	Safety Analysis Set
Table 6.2	Summary of Concomitant Antiepileptic Therapies	Safety Analysis Set
Table 6.3	Summary of Concomitant Antiepileptic Drugs	Safety Analysis Set
Table 6.4	Summary of Concomitant Rescue Medications	Safety Analysis Set
Table 6.5	Summary of Other Concomitant Medications	Safety Analysis Set
Table 7.1	Summary of Treatment Compliance	Safety Analysis Set
Table 7.2	Summary of IVRS Compliance	ITT Analysis Set
Table 8.1.1	Summary of TSC-associated Seizure Frequency	ITT Analysis Set
Table 8.1.2	Negative Binomial Regression Analysis of TSC-associated Seizure Count During Baseline and Treatment Periods	ITT Analysis Set
Table 8.2.1.1	Summary of TSC-associated Seizure Frequency	PP Analysis Set
Table 8.2.1.2	Negative Binomial Regression Analysis of TSC-associated Seizure Count During Baseline and Treatment Periods	PP Analysis Set

Table Number	Title	Analysis Set

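### SAP 5.7.1 sets no end date for a blinded-phase concomitant medication, so drugs started in the OLE or after the treatment period can enter the descriptive blinded medication tables.

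*SAP*

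**What the plan says.** SAP 5.7.1 (Concomitant Medication) has two limbs. Under the first, a medication is concomitant for a phase "if it has a start date on or after the first dose of IMP for the corresponding phase". The second limb adds drugs that began before that dose and had not been stopped. The section then asks for summaries of concomitant AEDs, rescue medications and other medications, one set per phase. In SAP Appendix 6 the blinded versions are Table 6.3 ("Summary of Concomitant Antiepileptic Drugs"), Table 6.4 (rescue) and Table 6.5 (other), all on the safety analysis set.

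SAP 5.4.3 (Demographic Data and Baseline Characteristics) relies on this definition. An AED recorded on both the history page and the concomitant page is removed from the prior count if 5.7.1 makes it concomitant for the double-blind phase. The same paragraph then adds: "AEDs starting after the last dose of IMP during the double-blind phase will not be counted".

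Protocol 8.2 bars new AEDs, including oral mTOR inhibitors, in the randomized phase but lets them be considered case by case in the OLE. Protocol 9.1.2 adds: "On-label use of mTOR inhibitors (for the treatment of seizures or tumors) and general anesthesia are permitted in the OLE phase of the trial". Protocol 9.1.1.12 collects concomitant medications at Visit 12, four weeks after Visit 11 or the final dose, for patients who withdraw or do not enter the OLE.

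**The concern.** The reference to the corresponding phase only selects which first dose applies. Every OLE start date is also later than the first blinded dose, so an OLE start satisfies the blinded rule as well as the OLE rule. So does a drug started after a patient has left the treatment period.

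The blinded medication tables are where a reader checks whether background and rescue drugs were similar between arms during randomized treatment. If OLE starts are mixed in, an AED properly added in the OLE looks like an addition the protocol barred. Starts made while every patient was on active drug would be displayed by randomized arm. Starts after withdrawal would add drugs to whichever arm lost more patients.

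The link to 5.4.3 carries the problem one step further. An AED tried before the trial and restarted in the OLE could be removed from the prior count because 5.7.1 calls it concomitant, and then be refused as current because it started after the last blinded dose. SAP 5.5.5 uses these counts for subgroups of the primary and 50% responder endpoints, cut at 5 prior AEDs and at 8 prior plus concurrent AEDs.

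**Working it through.** No figure in the plan depends on this rule, so there is none to reproduce. The check compares the SAP's phase rules and then works out how wide the open window is.

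**Phase limits in the SAP**

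| Rule | Start | End |
|---|---|---|
| 5.7.1 blinded concomitant medication | first blinded dose | none stated |
| 5.6.2 blinded treatment-emergent AE | first blinded dose | OLE Day 1 |
| 5.4.3 AED counts | – | last double-blind dose |
| 5.4.3 named-AED use | baseline | end of treatment period ("at any point during baseline period or treatment period") |
| 5.5.4.3 rescue-medication endpoint | Visit 3 | Visit 10 |

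The other four state an end. The cut-off in 5.4.3 comes straight after the reference to 5.7.1; it would have little to do if 5.7.1 already excluded late starts.

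**Width of the window.** Inputs: treatment period Day 1 to Day 113 (SAP 5.1.3.4). OLE Day 1 is expected on the end-of-treatment visit (SAP 5.1.2), so OLE day d is study day 113 + d − 1. Visit B6 is OLE Day 183, end of OLE treatment is OLE Day 365 and OLE follow-up is Day 403 (Protocol Appendix 1). Visit 12 is Day 151.

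- To Visit B6: 113 + 182 = 295 days, of which 182 (62%) fall after Day 113.
- To end of OLE treatment: 113 + 364 = 477 days, of which 364 (76%) fall after Day 113; 477/113 = 4.2.
- To OLE follow-up: 113 + 402 = 515 days, of which 402 (78%) fall after Day 113.
- Completer who does not enter the OLE: 151 days, of which 38 (25%) fall after Day 113.

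**Illustration.** The documents give no rate of new starts, so I assume a constant rate r per 28 days, from 0.5% to 5%. The share of patients with at least one new start by day D is 1 − exp(−r × D/28). For r = 1%, D = 113: 1 − exp(−0.0404) = 4.0%. For r = 1%, D = 477: 1 − exp(−0.1704) = 15.7%.

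| Assumed r per 28 days | True blinded start (Day 113) | Flagged, OLE data to Visit B6 (Day 295) | Flagged, OLE data to Day 477 | Flagged, OLE data to Day 515 |
|---|---|---|---|---|
| 0.5% | 2.0% | 5.1% | 8.2% | 8.8% |
| 1% | 4.0% | 10.0% | 15.7% | 16.8% |
| 2% | 7.8% | 19.0% | 28.9% | 30.8% |
| 5% | 18.3% | 41.0% | 57.3% | 60.1% |

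These percentages are for patients who enter the OLE and have records to the day shown. Protocol 13.2 has the blinded phase locked and unblinded before the OLE is complete, so many patients will have less OLE data than the last two columns assume.

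**Subgroup counts.** One AED lost from the prior count lowers the prior total and the prior-plus-concurrent total by 1. Only a patient at exactly 5 prior AEDs (5 − 1 = 4, now below 5) or exactly 8 in total (8 − 1 = 7, now below 8) changes subgroup.

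**The case against.** The best defence is that 5.7.1 speaks of each phase and asks for separate summaries. If OLE starts also counted as blinded, the blinded table would in effect cover the whole trial and the separation would mean little. Phase separation was very probably intended, and a programmer may apply a cut-off unprompted. That stands as a statement of intent, but the plan does not print the cut-off, and other sections of the same plan print theirs.

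Several further points stand and limit the reach:

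- Tables 6.3 to 6.5 are descriptive, and 5.7.1 lists start and stop days, so a late start can be seen.
- The cut-off sentence in 5.4.3 can be read as governing the whole AED derivation. An OLE record would then be ignored and would not remove an AED from the prior count. The subgroup problem arises only on the other reading, and then only for a patient who restarts a historical AED in the OLE and sits exactly on a cut. These subgroups lie outside the testing hierarchy.
- The adverse-event rule is only a partial model. OLE Day 1 does not exist for a patient who withdraws or declines the OLE, so 5.6.2 states no end for them either.
- Stopping the window at the last blinded dose would create a different problem. SAP 5.1.1.1 keeps treatment-period seizure data recorded after withdrawal in the primary analysis. AEDs started between stopping study drug and Day 113 bear on those data and should stay visible.

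A reader might infer that the open rule contaminates the efficacy results or the comparison of rescue use. The documents do not support that. The primary analysis does not use 5.7.1, the rescue-medication endpoint runs from Visit 3 to Visit 10, and the named-AED subgroups use the baseline and treatment periods. A reader might also extend the point to Table 6.2 (nerve stimulation and ketogenic diet), but 5.7.1 defines a concomitant medication, and it is less clear that it governs these therapies.

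**Conclusion.** The point holds as a gap in a stated rule. Taken at its words, 5.7.1 places OLE and post-treatment starts in blinded Tables 6.3 to 6.5 under the randomized arms. The effect on the prior-AED subgroups is possible but rare, and depends on how 5.4.3 is read.

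The window can be up to 477 days to the end of OLE treatment (515 to follow-up) instead of 113. A reader might take the ratio of 4.2 as the expected inflation of the tables. It is a ceiling: it needs a full OLE year of records in the data used for the blinded report, and the planned lock makes that unlikely for all patients. It also does not apply to drugs already in use at Day 1, which count under either reading. The illustrated percentages rest on assumed constant start rates.

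The change is worth making before the tables are produced because it is cheap and removes a real ambiguity. It does not put the trial's main conclusions at risk.

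**What to change.** In SAP 5.7.1, state that a medication is blinded-phase concomitant only if it was taken between the first blinded dose and the end of the blinded treatment period. For patients who enter the OLE, that end is before the first OLE dose; for all others it is Day 113. Within that window, show medications started after the patient stopped study drug as a separate category, so that they remain visible beside the seizure data still used in the primary analysis. Assign later starts to the OLE or to a post-treatment category. Say whether the same limits apply to the therapies in Table 6.2.

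In SAP 5.4.3, use the bounded definition when removing an AED from the prior count. Make the removal apply only to records that 5.4.3 goes on to count as current, so that no AED is lost from both counts, including one restarted between the last blinded dose and Day 113.

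The cost is a short SAP edit, one date condition in the medication programs and one extra category in the tables. No new data are needed.
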